#### **14.4.3 Analysis Methods**

The change in overall pain VAS as well as overall pain VAS at both baseline and the 3-Month visit will be summarized using descriptive statistics, (e.g., mean, standard deviations, etc.). The 95% CI of the mean change will be calculated.

In addition, percentage of change in overall pain VAS will be calculated using change in overall pain VAS divided by overall pain VAS at baseline. A negative percentage of change in VAS is a percentage of reduction in VAS, thus an improvement. The percentage of change in overall pain VAS will be summarized using descriptive statistics, (e.g., median and inter-quartile range, etc.)

#### **14.4.4 Determination of Subjects/Data for Analysis**

The primary analysis will use subjects who are implanted with Intellis neurostimulator, follow DTM-LE SCS programming, and provide outcome measures at both baseline and 3-Month visit (Per-protocol Analysis set).

Two sensitivity analyses will be performed, one uses Completers Analysis Set and one uses Implanted Analysis Set. The sensitivity analysis of all implanted subjects will be performed using MI method for missing data at the 3-Month Visit. For scheduled 3-Month visit, if an Unscheduled Visit occurred within the 3-Month visit window, and the VAS is collected at the Unscheduled Visit, the VAS from the Unscheduled Visit will be used in the analysis of the 3-Month visit. Otherwise, the missing VAS will be imputed using MI. Prior to the use of MI, the distributions of the continuous variables will be assessed for normality and transformation may be considered if they are not normally distributed. The model variables in MI will include study site, subject age, gender, primary diagnosis, VAS at baseline, 1-Month visit. The fully conditional specification method with 10 burn-in iterations within SAS and 10 repetitions ( $M = 10$ ) will be used for imputation. Constraints will be set so that the imputed VAS are restricted to values ranging from 0-10. Following imputation, the objective will be evaluated using MI analysis method.

### **14.5 Secondary Objective**

To characterize programming parameters associated with energy use from Device Trial through 12-Month visit.

#### **14.5.1 Hypothesis**

There is no hypothesis testing for the secondary objective. The secondary objective is to characterize programming parameters associated with energy use.

#### **14.5.2 Endpoint Definition and derivation**

Subject's programmed settings (frequency, pulse width, and amplitude) together with the impedance range measurements and cycling ON-OFF time will be summarized.

**14.5.3 Analysis Methods:**

The programming parameters associated with energy use will be summarized using descriptive statistics, (e.g., mean, standard deviations, etc.) from Device Trial through 12-Month visit. Where possible, the energy use may be summarized by average recharge interval.

**14.5.4 Determination of Subjects/Data for Analysis**

The analysis will use subjects who contribute to follow-up visits.

**14.7 Safety assessment**

To characterize all device-related, therapy-related, and procedure-related adverse events and device deficiencies from the Device Trial Start Visit until study exit. Adverse events and device deficiencies will be summarized using summary tables displaying the frequency and percentages. Adverse events will be summarized by seriousness as well.

## 14.8 Sample Size Justification

The statistical software PASS 11 was used for sample size and precision calculation at 95% confidence level (2-sided) using the Confidence Intervals for One Mean module. The precision estimates (the distance from mean to limits) by sample size and standard deviation of VAS are provided in Table 14-1. Assuming a standard deviation of 2.6 based on internal historical studies, a sample size of 30 subjects provides an expected precision of 0.97.

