Statistics	
The Confidence Intervals for One Mean module in statistical software PASS 11 was used to provide the following sample size justification: a sample size of 30 subjects produces a two-sided 95% confidence interval with a distance from the mean to the limits that is equal to 0.97 when the estimated standard deviation is 2.6.
 
With estimated attrition of 40% between enrollment and implant and 10% between implant and 3-Month, to achieve approximately 30 subjects at 3-Month visit, up to 56 subjects may be enrolled into the study.
 
For the primary objective, the mean change of overall pain intensity from baseline to 3-Month visit will be reported with a 95% confidence interval (CI). Primary analysis will use per-protocol analysis set who are implanted, follow DTM-LE SCS programming, and provide data at both baseline and 3-Month visits. Sensitivity analyses will use completers analysis set who are implanted and provide data at both baseline and 3-Month visits regardless of

	
programming patterns, as well as implanted analysis set with multiple imputation (MI) for missing data.
 
The secondary objective will be analyzed with descriptive statistics from Device Trial to 12-Month visit. Subjects who contribute to follow-up visits will be included in the analysis.
 
[REDACTED]
 
Adverse events and device deficiencies will be summarized using summary tables displaying the frequency and percentages. Adverse events will be summarized by seriousness as well.

--	---

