### **10.13 Unscheduled Visits**

Unscheduled visits may occur if programming changes are required to correct programming errors, to reprogram to optimize pain control, or as needed for an AE or DD. Whenever feasible, subjects should have their devices interrogated. Imaging may be performed to assess for lead migration if deemed necessary by the investigator and subjects may be re-programmed, if necessary.

The following information may be collected at unscheduled follow-up visits:

- VAS
- Reason for the visit
- Programming parameters/device interrogation report(s) with initial and final settings
- Imaging (if performed)
- Changes to pain medications
- AEs/DDs

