**Table 14-1: Precision by Sample Size and Standard Deviation of VAS**

Sample size (N)	Standard deviation (S)			
	2.4	2.6	2.8	3.0
26	0.97	1.05	1.13	1.21
28	0.93	1.01	1.09	1.16
30	0.90	0.97	1.05	1.12
32	0.89	0.94	1.01	1.08

With estimated attrition of 40% between enrollment and implant and 10% between implant and 3-Month from historical internal and external pain studies, to achieve approximately 30 subjects at 3-Month visit, up to 56 subjects may be enrolled into the study.

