**Figure 5-1: Study Visit Diagram**

## 6. Determination of Sample Size

The statistical software PASS 11 was used for sample size and precision calculation at 95% confidence level (2-sided) using the Confidence Intervals for One Mean module. The precision estimates (the distance from mean to limits) by sample size and standard deviation of VAS are provided in Table 6-1. Assuming a standard deviation of 2.6 based on internal historical studies, a sample size of 30 subjects provides an expected precision of 0.97.

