## 7.10 Safety Evaluation

All device-related, therapy-related, and procedure-related adverse events and device deficiencies from the Device Trial Start Visit until study exit will be characterized.

Adverse events and device deficiencies will be coded and summarized using the most recent version of Medical Dictionary for Regulatory Affairs (MedDRA).

The adverse events will also be categorized by relationship to study device and/or therapy. Adverse events will be presented in summary tables displaying the number of serious events, the number of events, and the number and percentage of subjects with one or more events. A summary of all device or therapy related adverse events and of any deaths will also be provided. A narrative of each serious device- or therapy-related adverse event will be provided.

Device deficiencies will be presented in summary tables displaying the number of deficiencies, and the number and percentage of subjects with deficiencies.

Device exposure will be summarized by analysis set and is considered from the time the subject is first exposed to the neurostimulation system (at the beginning of the device trial) until the product is explanted, or the subject discontinues from or completes the study, if later. Amount of exposure will be summarized (in months) using descriptive statistics such as mean, standard deviation, minimum, and maximum.

Data from the Scheduled Follow Up CRF will be evaluated for subjects in the Completer Analysis Set to determine whether subjects were programmed within DTM-LE limits during the study. For subjects who

were programmed within DTM-LE limits, the months of DTM-LE exposure will be computed in the same way as above, with the Cut-off Date for DTM-LE extending until the date at which it was reprogrammed out of DTM-LE limits.

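### Does the 0.97 precision, worked out for about 30 subjects with 3-Month data, misstate what the smaller Per-protocol set will deliver?

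*Protocol*

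**What the plan says.** Protocol 14.8 states: "Assuming a standard deviation of 2.6 based on internal historical studies, a sample size of 30 subjects provides an expected precision of 0.97". SAP section 6 repeats it: "a sample size of 30 subjects provides an expected precision of 0.97". Both print the same table of half-widths for N = 26, 28, 30 and 32 and SD 2.4 to 3.0 (Protocol Table 14-1, SAP Table 6-1).

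The enrolment figure allows for 40% loss before implant and 10% from implant to 3 months: "to achieve approximately 30 subjects at 3-Month visit, up to 56 subjects may be enrolled into the study".

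The set for the primary interval is given in Protocol 14.4.4: "The primary analysis will use subjects who are implanted with Intellis neurostimulator, follow DTM-LE SCS programming, and provide outcome measures at both baseline" and the 3-Month visit. SAP 7.9.1.4 sets the same conditions. The Completers set has the same data requirement without the programming condition; the synopsis (Statistics) says "Sensitivity analyses will use completers analysis set who are implanted and provide data at both baseline and 3-Month visits regardless of" programming patterns.

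SAP 7.10 says that follow-up data will be "evaluated for subjects in the Completer Analysis Set to determine whether subjects were programmed within DTM-LE limits during the study". It counts DTM-LE exposure "with the Cut-off Date for DTM-LE extending until the date at which it was reprogrammed out of DTM-LE limits".

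There is no hypothesis test for the primary objective (Protocol 14.4.1, SAP 7.9.1.1).

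**The concern.** The 30 behind the 0.97 is defined by having data at 3 months. That describes the Completers set, which serves only a sensitivity analysis. The primary interval comes from the Per-protocol set, a subset of completers, so its N cannot be larger and may be smaller. The two attrition steps contain nothing for subjects who leave DTM-LE programming, although SAP 7.10 provides for that case and Protocol 10.13 permits reprogramming between visits: "Unscheduled visits may occur if programming changes are required to correct programming errors, to reprogram to optimize pain control".

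Because the study is descriptive, this half-width is the whole sample-size justification. A reader could take 0.97 as the expected precision of the primary result when the primary set may give something wider. A table cell that does not follow from the formula adds to the doubt about the calculation.

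**Working it through.** **Inputs.** Two-sided 95% interval for one mean, SD 2.6, N = 30 (Protocol 14.8, SAP 6); attrition of 40% and 10% and a ceiling of 56 enrolled (text under Table 14-1). The rate of exclusion for programming is not given in either document, so the exclusion counts below are assumptions.

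**The plan's own figures.** Half-width = t(0.975, N-1) x SD / sqrt(N).

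- N = 30, SD 2.6: 2.0452 x 2.6 / sqrt(30) = 0.971. The stated 0.97 reproduces. Using the normal quantile instead gives 0.930, so the table uses t.
- Enrolment: 30 / (0.60 x 0.90) = 55.6, rounded up to 56. Conversely, 56 x 0.60 = 33.6 implanted, and 33.6 x 0.90 = 30.2 with 3-Month data.

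**If some of the 30 completers drop out of the Per-protocol set (SD 2.6).**

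| Excluded (assumed) | N | Half-width | Ratio to N = 30 |
|---|---|---|---|
| 0 | 30 | 0.971 | 1.000 |
| 1 | 29 | 0.989 | 1.019 |
| 2 | 28 | 1.008 | 1.038 |
| 3 | 27 | 1.029 | 1.059 |
| 4 | 26 | 1.050 | 1.082 |
| 5 | 25 | 1.073 | 1.105 |
| 6 | 24 | 1.098 | 1.131 |

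Losing 6 of 30 (20%) therefore costs 1.10 - 0.97 = 0.13 on the 0 to 10 scale. The printed rows for N = 28 and N = 26 already cover up to 4 of 30 (13%).

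**Compared with the uncertainty already in the table.** At N = 30, moving the SD from 2.4 to 3.0 takes the printed half-width from 0.90 to 1.12, a wider range than any exclusion count above produces. At SD 2.4 the N = 26 cell is 0.97, so a slightly smaller SD would offset four exclusions. At SD 2.6 the N = 32 cell is 0.94. If post-implant attrition were 5% instead of 10% (an assumption), 56 x 0.60 x 0.95 = 31.9 subjects would have 3-Month data. So 0.97 is a lower bound for the primary interval only at SD 2.6 and the planned attrition.

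**How likely is exclusion before the primary measurement?**

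- 1-Month visit (Protocol 10.12.1): reprogramming for insufficient relief is confined to stated limits.
- 3-Month visit (10.12.2): reprogramming depends on the VAS taken at that visit, so it comes after the primary measurement.
- Unscheduled visits (10.13): reprogramming is allowed; the section does not say that it may go outside the limits.
- SAP 7.10 sits in the safety section and covers exposure up to 12 months. It does not say that departures are expected before month 3.

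**Table check.** The t formula reproduces 15 of the 16 cells to two decimals. The exception is N = 32, SD 2.4: 2.0395 x 2.4 / sqrt(32) = 0.865, which rounds to 0.87 where both documents print 0.89. The normal quantile gives 0.832, so it does not explain the printed value either. The cell lies outside the N = 30 row and the SD 2.6 column.

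**The case for a change.** The best argument for changing the text is that the sponsor has defined two distinct sets, made the narrower one primary, and then justified the sample size with the count for the wider one. Precision is the only justification offered, and it appears in the synopsis, in Protocol 14.8 and in SAP 6 without saying which set it describes. The N = 28 and N = 26 rows are printed, but no text links them to the Per-protocol set. Weekly calls up to month 3 look for inadequate relief (Protocol 10.11), so some departures before the endpoint are possible. A sentence would cost almost nothing.

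Part of this stands. The 30 is a completer count, the Per-protocol set is a subset of it, and no allowance is made for programming. Early departures cannot be ruled out either: the detailed set definitions (Protocol 14.1.1, SAP 7.1.3) and the programming limits are not visible in the public copies, so how strictly the programming condition is applied, and over what period, cannot be checked.

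What does not stand is that this amounts to a shortfall. The plan promises about 30 subjects at 3 months, and its attrition figures deliver 30.2. It makes no promise of 30 in the Per-protocol set. A planned range such as N = 28 to 24 would have no source in the documents and would give an invented exclusion rate the appearance of a planning figure.

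**Conclusion.** No change to the plan is needed. The sample-size statement is true on its stated terms, N = 30 and SD 2.6, and a reader who wants the precision of a smaller Per-protocol set can read 1.01 or 1.05 from the table as printed. At SD 2.6, with 30 completers and assumed exclusions of 1 to 6, the primary half-width would be 2% to 13% wider than 0.97, or 0.02 to 0.13 on the 0 to 10 scale. The result will be reported with its actual N and interval, and since there is no hypothesis test, precision target or decision rule, no conclusion turns on that difference. Extra explanatory text would alter neither enrolment, endpoint, analysis set nor what the study can show.

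The 0.89 in both tables is a clerical slip for 0.87 that can be put right whenever the documents are next revised; no design figure relies on it.

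This conclusion rests on the set definitions visible in the synopsis, Protocol 14.4.4 and SAP 7.9.1.4, and on exclusions staying within the assumed range. A much larger loss, say 30% (N = 21, half-width 1.18), would be more noticeable, but nothing in the visible documents points to one.

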**Table 14-1: Precision by Sample Size and Standard Deviation of VAS**

Sample size (N)	Standard deviation (S)			
	2.4	2.6	2.8	3.0
26	0.97	1.05	1.13	1.21
28	0.93	1.01	1.09	1.16
30	0.90	0.97	1.05	1.12
32	0.89	0.94	1.01	1.08

With estimated attrition of 40% between enrollment and implant and 10% between implant and 3-Month from historical internal and external pain studies, to achieve approximately 30 subjects at 3-Month visit, up to 56 subjects may be enrolled into the study.

## 14.9 Minimization of Bias

Selection of subjects, treatment of subjects, and evaluation of study data are potential sources of bias. Methods incorporated in the study design to minimize potential bias include (but are not limited to):

- Missing data are a potential source of bias when analyzing study data. A rigorous study design and execution will help prevent the incidence of missing data from occurring. All efforts will be made to ensure patient follow-ups are completed with limited attrition to ensure interpretability of study results.
- To reduce the possibility of atypical results from a site overly influencing the combined results, the maximum number of subjects to be enrolled at a single study site is limited to 10 and cannot be increased without prior sponsor approval.

In summary, potential sources of bias that may be encountered in this study have been considered and minimized by careful study design.

## 15. Ethics

### 15.1 Statement(s) of Compliance

The DTM-LE SCS study will be conducted in accordance with this protocol, the ethical principles that have their origin in the Declaration of Helsinki, all applicable regulatory requirements (21CFR§50 Protection of Human Subjects, 21CFR§56 IRB, and 21CFR§803 Medical Device Reporting) and will comply with the concepts of Good Clinical Practices (GCP). The principles of the Declaration of Helsinki have been implemented in this study by means of the patient informed consent process, IRB approval, risk benefit assessment, study training, clinical trial registration on <http://clinicaltrials.gov/>, and publication policy. Study Investigators will be required to sign an Investigator Agreement stating their intent to adhere to applicable regulations.

The study will not begin at any site until an IRB letter approving the protocol, the IC, and any other subject-facing documents is received by Medtronic.

## **16. Study Administration**

### **16.1 Monitoring**

It is the responsibility of Medtronic to ensure proper monitoring of this study. Trained Medtronic personnel or delegates appointed by Medtronic may perform study monitoring at the study site in order to ensure that the study is conducted in accordance with the CIP, the CTA, and the applicable regulatory and local requirements. Medtronic, or delegates, must therefore be allowed direct access to the subjects' case histories (clinic and hospital records, and other source data/documentation) upon request as per the IC, Research Authorization (where applicable) and CTA. The principal investigator should also be available during monitoring visits.

#### **16.1.1 Monitoring Visits**

Frequency of monitoring visits may be based upon subject enrollment, study compliance, number of adverse events, number of deviations, observations from previous monitoring visits and any suspected inconsistency in data that requires investigation. Regulatory documents will be reviewed at each study site. Monitoring for the study, including site qualification visits, site initiation visits, interim monitoring visits, and closeout visits, will be done in accordance to the study-specific monitoring plan.

Monitoring visits may be conducted periodically to assess study site progress, the investigator's adherence to the CIP, regulatory compliance including but not limited to IRB approval and review of the study, maintenance of records and reports, and review of source documents against subject CRFs in accordance to the study-specific monitoring plan. Monitors review study site regulatory and study compliance by identifying observations of non-compliance and communicating those observations along with recommendations for preventative/corrective actions to study site personnel. Monitors may work with study personnel to determine appropriate corrective action recommendations and to identify trends within the study or at a particular study site.

### **16.2 Data Management**

This study will use the Oracle Clinical Remote Data Capture (RDC) system, which allows the study sites to enter data directly to the eCRF in the sponsor's database over a secure internet connection. This system is fully validated and controls user access, ensures data integrity, and maintains audit trails. User access to the RDC system will be granted to each individual based on his or her delegation of authority. If a person only authorized to complete eCRFs makes changes to an already signed eCRF, the system will require the investigator, or authorized delegate, to re-sign the eCRF. The principal investigator will ensure that only appropriately delegated study personnel are given access to the electronic eCRF system; user IDs and passwords may not be shared.

Procedures in the CIP require source documentation. Source documentation will be maintained at the study site. Source documents, which may include worksheets, subject medical records, programmer printouts, and interrogation files, must be created and maintained by the investigational study site team.

The principal investigator is responsible for the overall quality (completeness and accuracy) of the data entered on the eCRFs and in all other required reports. The data reported on the CRFs shall be derived from source documents and be consistent with these source documents, and any discrepancies shall be explained in writing. See [Section 10.19](#) for CRFs and data collection elements that may be considered source.

Sponsor personnel will perform routine edit and consistency checks, in-house and during monitoring visits, for items such as missing data or inconsistent data. Identified data inconsistencies will be resolved by use of data queries; investigators and site personnel will review data queries and respond to them in a timely manner. The resolved discrepancy will become a part of the eCRF record for the subject. At the end of the study, the data will be frozen and will be retained indefinitely by Medtronic. All records and other information about subjects participating in this study will be treated as confidential.

### **16.3 Direct Access to Source Data/Documents**

Source data are defined as all information in original records, certified copies of original records of clinical findings, observations, or other activities in a clinical investigation necessary for the reconstruction and evaluation of the clinical investigation. A source document is a printed, optical, or electrical document containing source data. Examples of source documents include the following: hospital records, laboratory notes, device accountability records, photographic negatives, radiographs, records kept at the investigational site, and at laboratories involved in the clinical investigation.

The principal investigator is responsible for ensuring source data and documents are complete, legible and accurate; and entries are made in a timely manner by appropriately delegated study staff.

The principal investigator and site personnel will provide the Medtronic monitor(s) with direct access to source data that support the data on the CRFs as well as other documentation supporting the conduct of the study.

Medtronic or third-party auditors representing Medtronic may perform Quality Assurance audits to verify the performance of the monitoring process and study conduct, and to ensure compliance with applicable regulations. Representatives for regulatory bodies, such as the FDA, may also perform site inspections related to this clinical study. The principal investigator, site personnel, and institution will provide auditors with direct access to primary source data and all study-related documentation. Medtronic will investigate suspected cases of fraud or misconduct as appropriate.

